13.2 Treatment Exposure

Extent of exposure will be calculated in days using the following:

Extent of Exposure (days) = [Date of last dose – Date of first dose] + 1

Extent of treatment exposure (days) and the total number of doses received for each subject exposed to IMP will be summarized with continuous descriptive statistics using the Safety set. A subject listing of treatment exposure will also be produced.

14. Analysis of the Primary Endpoint

The primary endpoint is the mean change from baseline (Visit 2 / Day 1) to end of treatment (Visit 8 / Day 43) in BCVA letter score of the study eye as measured by the ETDRS testing method using the Evaluable set. BCVA will be measured at the beginning of every study visit and change from baseline for each subject will be calculated as follow-up visit minus baseline visit. Quantitative summary statistics will be used to summarize the BCVA letter score and change from baseline at each visit. A two-tailed, one-sample t-test will be used to assess the mean change from baseline in BCVA letter score at each visit, in which the change from baseline BCVA letter score will be compared to a reference value of zero. The following SAS code will be used to run the one-sample t-test:

```
PROC TTEST H0=0 ALPHA=0.20 DATA=INDATA;
  VAR BCVA_CHG;
RUN;
```

where

- *INDATA* is the name of the input dataset;
- *BCVA_CHG* is the change in BCVA from baseline to the follow-up visit.

A mixed model accounting for repeated measures will also be used to analyze BCVA. This model will include the change from baseline in BCVA letter score as the response variable and baseline BCVA letter score, smoking status and visit as explanatory variables for adjustment. LS means for each visit will be calculated along with corresponding 95% CIs and p-values. SAS code to implement this repeated measures mixed model is as follows:

```
PROC MIXED DATA=INDATA;
  CLASS SUBJID SMOKE VISIT;
  MODEL CHG = BASELINE SMOKE VISIT / DDFM = KR SOLUTION;
  REPEATED VISIT / SUBJECT=SUBJID TYPE=UN;
  LSMEANS VISIT / CL;
RUN;
```

where

- *INDATA* is the name of the input dataset sorted by *SUBJID* and *VISIT*;
- *SUBJID* is the subject ID number;
- *SMOKE* is the subject's smoking history (Never smoked, Ex-smoker, Currently smokes);

- *VISIT* is the visit at which the BCVA letter score was collected;
- *CHG* is the change from baseline in the BCVA letter score;
- *BASELINE* is the baseline BCVA letter score;

The Kenward-Roger method will be used to determine denominator degrees of freedom. An unstructured variance-covariance matrix will be used for the above repeated measures model. If the model does not converge using the unstructured matrix, the first order autoregressive structure and the compound symmetry structure will be employed, in that order.

The above analyses will be repeated on the PP set as a sensitivity analysis.

Additionally, the number of subjects with change from baseline in BCVA letter score for the following categories will be summarized with counts and percentages:

- ≥ 15 letters;
- ≥ 14 and ≥ 10 letters;
- ≥ 9 and ≥ 5 letters;
- ≥ 4 and ≥ -4 letters;
- ≥ -5 and ≥ -9 letters;
- ≥ -10 and ≥ -14 letters;
- ≤ -15 letters.

BCVA results will also be presented in a data listing. BCVA results in the fellow eye are not included in the analyses but will be included in the listings. BCVA will also be summarized by visit using box plots.

15. Analysis of the Secondary Endpoints

The analyses for secondary endpoints (incidence, seriousness and severity of AEs) will be discussed in the next section as part of the safety analyses. There is no secondary efficacy endpoint for the study.

16. Safety Analyses

Safety will be assessed for the following endpoints using the Safety set:

- Incidence, seriousness, and severity of AEs;
- Observed slit-lamp biomicroscopy values;
- Observed intraocular pressure (IOP) values;
- Changes from baseline in clinical laboratory values;
- Changes from baseline in physical examination;
- Changes from baseline in vital signs.

Adverse events will be presented using frequencies and percentages of subjects.

Other safety endpoints including slit-lamp biomicroscopy, IOP, clinical laboratory values, physical examination, and vital signs will be summarized using descriptive statistics. Changes or shifts from baseline will also be summarized where appropriate. Assessments performed by eye (study eye and fellow eye) will be summarized separately. No statistical inferential testing will be performed for safety variables.

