**PROTOCOL SUMMARY**

**Title:** A Single Arm Open-Label Study to Evaluate the Therapeutic Effects and Safety of a 6-Week Treatment Regimen of ALK4290 in Patients with Refractory Wet Age-Related Macular Degeneration (wAMD)

**Précis:** This study is designed to evaluate the therapeutic effects and safety of oral ALK4290 administered at 800 mg daily over a 6-week dosing period in subjects with refractory wAMD following treatment with intravitreal (IVT) anti-vascular endothelial growth factor (anti-VEGF). The study agent will be self-administered orally. Training on study agent administration will be conducted prior to initial study agent administration (at Visit 2) under the supervision of study personnel. All study agent administrations at the study site will be done under the direct supervision of the study personnel for documentation of precise administration times.

All subjects will undergo a screening visit, baseline/treatment visit(s), an end of study/early termination visit, and follow-up visits, as applicable. Visits will include safety and tolerability assessments, best corrected visual acuity (BCVA) as measured by the Early Treatment Diabetic Retinopathy Study (ETDRS) testing method, and morphological evaluations utilizing spectral domain optical coherence tomography (SD-OCT) and fundus photography/fluorescein angiography (FA). For a complete listing of study events, please see [Section 15.1, Schedule of Events Table](#).

**Objectives:** The primary objective of the study is to investigate the potential therapeutic effects of a 6-week, twice daily oral dosing regimen of ALK4290 on BCVA, as measured by ETDRS, in subjects with refractory wAMD following treatment with IVT anti-VEGF. As a secondary objective, the study will assess the safety of the proposed dosing regimen. The exploratory objectives are to investigate the potential pharmacokinetic and ocular morphological effects related to twice daily treatment of ALK4290 in refractory subjects with wAMD by measuring changes in concentrations of ALK4290 in plasma at various time points as well as central subfield thickness (CST), intraretinal fluid (IRF), subretinal fluid (SRF), and pigment epithelial detachment (PED) identified by SD-OCT and fundus photography/FA. Additionally, pharmacogenomic and biomarker evaluations will be conducted on blood and plasma samples.

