**5.3.2 HANDLING OF PARTICPANT WITHDRAWALS OR TERMINATION**

Approximately 30 subjects will be enrolled in the study. Subjects will be encouraged to complete the study and all assessments. However, subjects may voluntarily withdraw at any time, and the investigator may discontinue individual subjects from the study at any time. For subjects who withdraw consent from the study, no study procedures will be done thereafter. For those that withdraw from receiving the study agent, follow-up visits and the safety phone follow-up, are to occur per the protocol. Excluding cases of medical emergency but prior to the discontinuation of a subject from the clinical study for disease worsening, the study investigator should discuss each case of discontinuation with the sponsor and/or the medical monitor.

- The subject withdrawal criterion below should be used to assess worsening or disease progression. In such cases, a documented assessment by the principal investigator is required, and subjects with clinically significant disease progression should be considered for withdrawal from the study and subsequent initiation of standard of care:
- A BCVA loss of  $\geq 5$  letters from baseline
  - New macular subretinal hemorrhage
  - Investigator discretion based on acute worsening of underlying disease or substantial risk to further participation in the study

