## 8.2.3 END OF TREATMENT

All end of treatment (EOT) study-related procedures will be conducted at the conclusion of 6 weeks of treatment on Day 43 ±1. However, for subjects who withdraw consent from the study, no study procedures will be done thereafter. For subjects that withdraw from the study agent, EOT procedures and follow-up visits are to occur as per the protocol. Excluding cases of medical emergency, but prior to the discontinuation of a subject from the clinical study for disease worsening, the study investigator should discuss each case of discontinuation with the sponsor.

### 8.2.3.1 Visit 8

At Visit 8, the following procedures and assessments are performed:

- Pharmacokinetic and biomarker samples are taken
- All ophthalmological assessments: BCVA, SD-OCT, fundus photography/FA, slit lamp, and IOP
- Vital signs, physical examination, safety laboratory tests, **Poland only**: serum pregnancy test (in women of childbearing potential), and 12-lead ECG

- Review of concomitant medications
- AE reporting and evaluation

---

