#### 8.2.4 FOLLOW-UP VISITS

Follow-up visits will be performed after Visit 8 for all subjects who had at least one dose of trial treatment. Follow-up visits will not be performed if:

- The subject is lost to follow-up
- The subject withdraws consent from the study
- The investigator and sponsor agree not to pursue further follow-up visits with the subject
- The subject dies

In these cases, the trial completion page of the eCRF must be filled out.

##### 8.2.4.1 Visit 9

At Visit 9, the following procedures and assessments are performed:

- Pharmacokinetic and biomarker samples are taken
- Specified ophthalmological assessments: BCVA, SD-OCT, slit lamp, and IOP
- Vital signs and safety laboratory tests
- Review of concomitant medications
- AE reporting and evaluation

##### 8.2.4.2 Visit 10

At Visit 10, the following procedures and assessments are performed:

- Specified ophthalmological assessments: BCVA, SD-OCT, slit lamp, and IOP
- Vital signs, physical examination, and safety laboratory tests
- Review of current medications
- AE reporting and evaluation

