- A pre-dose pharmacokinetic (PK) blood sample will be taken to be centrifuged for collection of plasma samples. Biomarker plasma aliquots will be obtained from the pharmacokinetic (PK) samples. At Visit 2 only, four post-dose pharmacokinetic blood samples will be taken.
- A pre-dose PK blood sample will be taken to be centrifuged for collection of plasma samples.
- End of Treatment (EOT) visit (Visit 8): all study related procedures will be conducted at the conclusion of 6 weeks of treatment on Day 43 ±1. Withdrawal of consent is allowed at any time. For subjects who withdraw consent from the study, no study procedures will be done thereafter. For those that withdraw from the study agent, follow-up visits are to occur as per the protocol. Excluding cases of medical emergency, but prior to the discontinuation of a subject from the clinical study for disease worsening, the study investigator should discuss each case of discontinuation with the sponsor.
- Adverse events and concomitant medications will be assessed at every study visit as well as recorded at any unscheduled subject contact (e.g., unscheduled phone calls, etc.). Following completion of study agent treatment (Visits 2-8), all current medications will be assessed in the follow-up period.
- Pregnancy test required in **Poland only** per Inclusion Criteria.

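### The primary BCVA test uses only Day 43 values observed in the Evaluable set, while letter loss is a ground for considering study withdrawal, and no planned analysis of mean BCVA change covers all treated subjects

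*SAP*

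**What the plan says.** - **Endpoint and set.** SAP 14 takes the change from Visit 2 (Day 1) to Visit 8 (Day 43) "in BCVA letter score of the study eye as measured by the ETDRS testing method using the Evaluable set". It is compared with zero by a one-sample t-test, two-sided at 0.20 (SAP 3.4).
- **Missing values.** SAP 9.1 imputes dates only. SAP 9.3 maps Days 40 to 46 to Visit 8, so a BCVA taken earlier counts for an earlier visit.
- **Withdrawal.** Protocol 5.3.2 lists a BCVA loss of 5 or more letters among the criteria for worsening. After a documented assessment, "subjects with clinically significant disease progression should be considered for withdrawal from the study and subsequent initiation of standard of care".
- **Evaluable set.** Protocol 10.3 requires at least three weeks of treatment. SAP 6 allows replacement of those who discontinue before Day 22.
- **Other BCVA analyses.** SAP 14 adds a repeated-measures mixed model and repeats everything on the PP set, which protocol 10.3 makes a subset of the Evaluable set. The BCVA change tables (14.2.1.1 to 14.2.1.3) and the box plot use the Evaluable or PP set.
- **BCVA on wider sets.** Three outputs exist: baseline BCVA in Table 14.1.2 (ITT), losses of more than 15 letters counted as adverse events of special interest in Table 14.3.5 (Safety), and Listing 16.2.6.1 (ITT).
- **Assessment after stopping.** Protocol 8.2.3 states: "For subjects that withdraw from the study agent, EOT procedures and follow-up visits are to occur as per the protocol". Protocol 5.3.2 and the EOT footnote to 15.1 name only follow-up visits: "For those that withdraw from receiving the study agent, follow-up visits and the safety phone follow-up, are to occur per the protocol" and "For those that withdraw from the study agent, follow-up visits are to occur as per the protocol". Protocol 8.2.4 plans follow-up visits for all dosed subjects but waives them if "The investigator and sponsor agree not to pursue further follow-up visits with the subject". The Protocol Summary mentions "an end of study/early termination visit, and follow-up visits, as applicable", while the schedule in 15.1 has only Visit 8/EOT on Day 43.

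**The concern.** The variable being averaged helps to decide who is left to be averaged. Changes at successive visits are positively correlated, so a subject withdrawn for losing letters would be expected to sit below the group mean at Day 43. If that value is missing, the mean of those remaining moves up. There is no control arm in which the same selection could cancel, and the reference is a fixed zero.

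The selection can act twice. A subject who leaves before three weeks drops out of the Evaluable set and may be replaced. One who leaves later stays in the set but adds nothing to the Day 43 t-test. The only planned sensitivity set lies inside the Evaluable set, so it cannot reveal the problem.

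Protocol 2.2 says that a favourable BCVA effect could provide the basis for longer-term evaluation. A shift toward benefit therefore matters even in an exploratory trial.

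**Working it through.** **Inputs from the documents.** 30 enrolled, about 25 evaluable (SAP 6), an allowance of 5/30 = 16.7% for all causes; two-sided alpha 0.20, so 10% in the direction of improvement; visits on Days 8, 15, 22, 29, 36 and 43. The plan states no SD, measurement error, effect size or withdrawal rate, so there is no figure of its own to reproduce.

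**Step 1: arithmetic.** Let all 30 treated subjects have mean change 0, and let k of them, with mean −d, have no Day 43 value. The observed mean is then k·d/(30 − k).

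| k | d = 5 | d = 3 |
|---|---|---|
| 1 | 5/29 = +0.17 | 3/29 = +0.10 |
| 3 | 15/27 = +0.56 | 9/27 = +0.33 |
| 5 | 25/25 = +1.00 | 15/25 = +0.60 |

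For scale, with n = 25 and an SD of 5, the test is significant at 1.318 × 5/√25 = 1.32 letters.

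**Step 2: simulation.** Assumptions: 30 subjects; zero mean change; a random-walk true change with SD 4 or 6 at Day 43; independent error of SD 2 or 3 at baseline and at each visit. At Days 8 to 36 a subject with an observed loss of 5 or more letters is withdrawn with a fixed probability, set so that on average 1, 3 or 5 of 30 leave. No BCVA is taken afterwards, Evaluable means having the Day 22 visit, and nobody is replaced. The case of 5 uses up the plan's whole allowance.

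| Mean withdrawn | 1 | 3 | 5 |
|---|---|---|---|
| t-test bias, SD 4/error 2 | +0.18 | +0.56 | +0.94 |
| t-test bias, SD 6/error 3 | +0.22 | +0.68 | +1.17 |
| False improvement, SD 4/error 2 | 14% | 25% | 41% |
| False improvement, SD 6/error 3 | 13% | 21% | 32% |
| Mixed model on Evaluable, SD 4/error 2 | +0.05 | +0.16 | +0.28 |
| Mixed model on Evaluable, SD 6/error 3 | +0.08 | +0.21 | +0.36 |

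With no withdrawals the false-improvement rate was 10.1%. The same mixed model on all treated subjects gave a bias of −0.01 to +0.02 letters. If half of those withdrawn still attend Day 43, the t-test bias falls to +0.11/+0.35/+0.59 (SD 4) and +0.15/+0.43/+0.75 (SD 6).

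**Step 3: other assumptions.** With equal correlation of 0.5 or 0.8 between visits, SDs of 5 to 10, and 25% to 100% withdrawal at each visit with such a loss, the t-test bias ran from +0.7 to +6.9 letters and the Evaluable mixed model from +0.3 to +5.3. A likelihood analysis of all treated subjects stayed within about 0.13 of zero. Many of these cases lose far more subjects than the plan allows for. They confirm the direction and show that the size depends on the assumptions.

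**Step 4: natural decline.** Protocol 2.2 cites an average loss of 10 letters in a year without treatment. Taken as linear, that is 10 × 6/52 = 1.15 letters over six weeks. With this drift in Step 2, the bias hardly changes (+0.16/+0.53/+0.90 and +0.21/+0.64/+1.11), but false improvement falls to 1%/3%/7% and 2%/5%/10%.

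**The case against.** Several points on the other side stand.

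- **Withdrawal is discretionary.** Protocol 5.3.2 asks that it be considered, after a documented assessment and for clinically significant progression. A reader might infer that every subject who loses 5 letters leaves the analysis. The text does not say so.
- **Day 43 is planned for those who stop only the study agent.** Protocol 8.2.3 gives them EOT procedures. The other passages say less but do not contradict it. A reader might infer that Day 43 BCVA is lost for everyone who stops; the gap mainly concerns withdrawal from the study itself.
- **BCVA is not absent outside the Evaluable set.** A reader might infer that no BCVA result covers all treated subjects. The baseline summary, the count of losses above 15 letters and the listing do. What is missing is any summary or test of mean post-baseline change.
- **Some attrition is visible.** Tables show n at each visit, Table 14.2.1.3 shows letter-loss categories by visit, and Listing 16.2.3.2 names those excluded from analysis sets. In 30 subjects much can be traced by hand. However, worsening is not a named discontinuation reason in SAP 10, and protocol 7.2.1.2.1 and 7.2.1.2.5 differ on whether it is recorded as an adverse event.
- **The mixed model already helps.** In the 5-withdrawal cases of Step 2 it removes about 70% of the t-test bias.
- **The error rates assume zero mean change.** A reader might take 41% as the chance that an inert drug looks beneficial. Protocol 2.2 does not support that: vision is expected to decline without treatment, and Step 4 gives 1% to 10%. That decline describes untreated wAMD in general, not refractory disease, so it too is only an illustration.
- **The trial is exploratory.** It is unpowered, and no decision rule uses the p-value.

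**Conclusion.** The concern holds in conditional form. Where subjects are withdrawn from the study for letter loss and have no Day 43 BCVA, or leave before three weeks of treatment, the primary mean change is biased toward benefit, and no planned analysis of mean change covers all treated subjects. The direction needs only positive correlation between visits.

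The size cannot be known from the documents. For 1, 3 or 5 such withdrawals among 30, the illustrative shift in the t-test mean is about +0.2, +0.6 or +0.9 to +1.2 letters. Under a null of zero change, false improvement is then 13–14%, 21–25% or 32–41% against a nominal 10%. The Evaluable mixed model keeps +0.05 to +0.36. These figures rest on the assumed SDs and are not bounds. If withdrawal for worsening is rare, the bias is negligible.

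The text of SAP Section 8 and Clarification Memorandum #2 were not available. The part about early leavers therefore rests on the Evaluable definition in protocol 10.3. Priority is modest.

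**What to change.** 1. **SAP 14.** Keep the Evaluable t-test. Prespecify one sensitivity analysis that fits the already specified repeated-measures model to all treated subjects with a baseline and at least one post-baseline BCVA. Include subjects who were later replaced, exclude BCVA measured after another wAMD therapy starts, and report the result beside the primary one.
2. **SAP 10.** Tabulate disease worsening or BCVA loss as its own discontinuation reason.
3. **Protocol.** Reconcile 5.3.2, 8.2.3, 8.2.4 and the EOT footnote to 15.1 on whether Day 43 BCVA is collected after withdrawal for worsening. No change to the withdrawal criterion is proposed.

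Carrying the last observed change forward to Visit 8 is optional. In the Step 2 cases it was biased downward by 0.05 to 0.38 letters, so it could serve only as an unfavourable check.

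The cost is SAP wording, one further model run with its table, and one disposition row; no new patients are needed. The added estimate may be less favourable. It also assumes that values are missing at random given observed BCVA, which withdrawals for haemorrhage or at the investigator's discretion may violate.

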## 10 STATISTICAL CONSIDERATIONS

### 10.1 STATISTICAL DESIGN MODEL AND ANALYTICAL PLANS

The therapeutic effect of the treatment will be investigated in one single group of subjects, with no control group. The observed mean effect will be compared with 0 as reference value. Overall baseline and demographic data will be summarized using descriptive statistics.

Subject disposition (e.g., the number of subjects enrolled, completed, and discontinued) will be summarized and medical history data will be listed. Prior and concomitant medications taken from screening and during the study will be categorized by World Health Organization (WHO) classification for therapeutic class and drug name, listed and summarized by number and percentage of subjects.

Final analyses are not limited to the summaries described herein. Analytical details and assumptions will be fully presented in the SAP.

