3.4 Statistical Hypotheses

The null and alternative hypotheses for change from baseline in BCVA letter score as measured by ETDRS testing method are as follows:

H₀: Mean change from baseline in BCVA letter score at 6 weeks = 0

H₁: Mean change from baseline in BCVA letter score at 6 weeks ≠ 0

The hypothesis testing will be at a two-sided Type I error rate (α) of 0.20. Specifics of the statistical tests are provided in Section 14.

4. Study Design and Procedures

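### In this single-arm trial, the repeated-measures model's baseline-adjusted LS means carry standard errors that omit the sampling error of the mean baseline, so they are too small for the population mean change that SAP 3.4 tests

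*SAP*

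**What the plan says.** The design has one arm: "The therapeutic effect of the treatment will be investigated in one single group of subjects, with no control group" (Protocol 10.1). The null hypothesis is "Mean change from baseline in BCVA letter score at 6 weeks = 0" (SAP 3.4), a mean over the population and not a mean at a given baseline score. "The hypothesis testing will be at a two-sided Type I error rate (α) of 0.20" (SAP 3.4).

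SAP Section 14 analyses this hypothesis in two ways on the Evaluable set and repeats both on the Per Protocol set.

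- First: "A two-tailed, one-sample t-test will be used to assess the mean change from baseline in BCVA letter score at each visit", against zero.
- Second, a mixed model for repeated measures: "MODEL CHG = BASELINE SMOKE VISIT / DDFM = KR SOLUTION", with an unstructured covariance and "LSMEANS VISIT / CL". SMOKE has three classes. From this model, "LS means for each visit will be calculated along with corresponding 95% CIs and p-values".

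The LSMEANS statement has no option that sets the baseline value or the smoking weights. The defaults therefore apply: the observed mean baseline, and equal weight for each smoking class. SAP 17.1 says the quantitative imaging endpoints will be analysed much as the primary endpoint is.

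**The concern.** Baseline adjustment is useful in a comparison of arms, where the sampling error of the overall mean baseline cancels. Here there is no contrast for it to cancel from. With complete data, and leaving smoking aside, the LS mean at the sample's mean baseline is simply the raw mean change, so adjustment does not alter the estimate. The printed standard error nevertheless uses only the variance left after baseline is removed. It describes the mean change for subjects at this sample's mean baseline, taken as fixed. Kenward-Roger corrects for estimated covariance parameters; it does not restore the missing term.

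At stake are the coverage of the model's 95% CIs and the error rate of its p-values. These will stand beside the t-test results for the same hypothesis.

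**Working it through.** **Inputs.** About 25 evaluable subjects (SAP 6); α = 0.20 two-sided (SAP 3.4); 95% limits for the model (SAP 14). The documents give no SD, effect size or power, so there is no planned figure to reproduce. They also give no baseline-change correlation r, so r is assumed over a range.

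**Step 1: the missing term.** Let σ² be the variance of change, b the slope of change on baseline and s_x² the variance of baseline. The variance of the mean change splits as

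σ²/n = σ²(1 − r²)/n + b²s_x²/n, where b²s_x² = r²σ².

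The model reports only the first part. Model SE ÷ true SE = √(1 − r²).

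**Step 2: true size, one visit, no SMOKE, n = 25.** Under normality the model's statistic is a t variable on 23 df divided by √(1 − r²). True size is therefore 2·P(t₂₃ > c·√(1 − r²)), with c = 1.319 for nominal 0.20 and c = 2.069 for nominal 0.05.

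| r (assumed) | √(1 − r²) | SE too small by | True size at 0.20 | True size at 0.05 |
|---|---|---|---|---|
| 0 | 1.000 | 0% | 0.200 | 0.050 |
| −0.16 | 0.987 | 1% | 0.206 | 0.053 |
| −0.3 | 0.954 | 5% | 0.221 | 0.061 |
| −0.4 | 0.917 | 8% | 0.239 | 0.071 |
| −0.5 | 0.866 | 13% | 0.265 | 0.086 |

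A simulation of 20,000 trials gave 0.222, 0.235 and 0.265 at nominal 0.20 for the last three rows, and 0.061, 0.068 and 0.086 at nominal 0.05. The t-test on such data holds its nominal size.

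**Step 3: which r is plausible.** With equal variances at both visits, r = −√((1 − q)/2), where q is the baseline-to-follow-up correlation. Assumed q of 0.95, 0.90, 0.80, 0.70 and 0.50 give r of −0.16, −0.22, −0.32, −0.39 and −0.50.

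**Step 4: the repeated-measures model.** Simulated with 6 visits, n = 25, no SMOKE, complete data and approximate degrees of freedom. There were 400 runs per cell, so Monte Carlo error is about 1 point on coverage and 2 on size.

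- The LS mean equalled the raw visit mean (largest difference 0.0000).
- At |r| = 0.5 the model SE was 0.171 against a true SD of 0.199, and 95% coverage was 90.5%. Without BASELINE the SE was 0.197 and coverage 94.8%.
- At |r| = 0.3 the model SE was 0.189 against 0.208, with coverage 92.0%. Without BASELINE these were 0.198 and 93.8%.
- With dropout that depended on earlier change, at |r| = 0.5, the models with and without BASELINE had nearly the same spread (SD 0.199 and 0.202). Coverage was 92.0% and 95.0%.

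**Step 5: SMOKE.** Take an assumed split of 12/9/4, with smoking unrelated to change or baseline. Equal weighting multiplies the SE by f = √(25 × (1/12 + 1/9 + 1/4))/3 = 3.333/3 = 1.111.

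- Against the t-test SE, at r = −0.3: 1.111 × 0.954 = 1.06. The printed SE is larger.
- Against its own sampling SD: √[(1 − r²)f² / ((1 − r²)f² + r²)] = 0.96 at r = −0.3 and 0.89 at r = −0.5. The SE is still too small. Simulation gave 0.95 and 0.87 to 0.92.
- The 4 subjects in the smallest class are 4/25 = 16% of the sample but carry a third of the weight. If change differs by smoking class, the LS mean no longer estimates the population mean.

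**The case against.** **The model's interval need not look more precise.** A reader might infer that the model will show a tighter interval than the t-test and so produce a spurious significant result. The documents do not support that as a general statement, because the model contains SMOKE. Comparing 95% intervals from both methods, the simulated median width ratio (model to t-test) at r = −0.3 was 1.09 for a 12/9/4 split, 1.35 for 13/10/2 and 0.98 for 9/8/8. At r = −0.5 the ratios were 0.99, 1.23 and 0.89. These splits are assumptions. What remains is that the interval is too narrow for its own sampling variation.

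**The primary test is intact.** A reader might infer that the main BCVA test is compromised. It is not: SAP 14 lists the t-test first and the model as an additional analysis, and no decision rule uses the model's p-value. The study is not powered (SAP 6), and SAP 9.5 calls it exploratory. This stands and limits the importance of the point.

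**The error may be negligible.** If BCVA is highly repeatable, with q near 0.95, the SE is about 1% too small. This stands.

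**A conditional reading would make the SE valid.** For the mean change at this sample's mean baseline and with smoking classes weighted equally, it would be. SAP 3.4 does not state that target, and SAP 14 does not label the LS means as conditional.

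**The imaging endpoints.** A reader might infer that all of them inherit the problem. SAP 17.1 asks only for a similar analysis, and Protocol 7.2.5 disclaims specific inferential testing for them. They are affected only so far as this model is applied to them.

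**Conclusion.** The point holds for the model as coded. If change correlates with baseline, the LS-mean standard errors understate the uncertainty about the population mean change. The shortfall is about 1% at r = −0.16 and 13% at r = −0.5, and similar or somewhat smaller once SMOKE is included. It vanishes at r = 0. In the case without SMOKE, a nominal 0.20 test then has a true size between about 0.21 and 0.27. Size depends entirely on a correlation that the documents do not give; the mechanism does not. Separately, equal weighting over smoking classes makes the LS mean a different quantity from the one in SAP 3.4 when the classes are uneven and change differs between them.

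The defect lies in a supplementary analysis, its Per Protocol repeat, and any imaging endpoint analysed with it. It is modest, but it gives wrong error bars for the stated hypothesis and is cheap to remove.

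**What to change.** For the by-visit means, CIs and p-values, use `MODEL CHG = VISIT / DDFM=KR` with the same REPEATED statement, and state in SAP 14 that both BASELINE and SMOKE are dropped from this model. With complete data and the unstructured covariance it then agrees with the t-test; under the fallback structures the estimate still agrees, but the SE pools variance across visits. It keeps the repeated-measures handling of dropout: with dropout that depended on earlier change, the observed-case mean was biased by about +0.15 SD in simulation, and the model without BASELINE by about 0. Report the BASELINE and SMOKE effects from a separate, descriptive model. State in SAP 17.1 which model the imaging endpoints use.

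The cost is one line of code and a few sentences. The interval may become wider or narrower, depending on r and the smoking split. The covariates also no longer inform the handling of missing visits. When simulated dropout depended on baseline at |r| = 0.5, bias was −0.019 without BASELINE, −0.004 with it, and −0.131 for the observed-case mean.

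Modelling the BCVA score itself at Visits 2 to 10 and taking Visit 8 minus Visit 2 is not recommended here: an unstructured covariance over 9 visits has 9 × 10/2 = 45 parameters for about 25 subjects.
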